#### 1.3.2.2 Dose escalation

Dose escalation will start with 0.25 mg. Decreasing escalation factors, from 3 to 1.25, between dose escalating steps will be applied up to the highest planned dose of 50 mg. As noted above, the doses will progress only as long as the maximal acceptable systemic exposure has not been reached.

As long as the pre-defined maximum systemic exposure has not been reached, higher doses than the expected therapeutic dose of 2 mg may be justified for the following reasons:

First, subsequent clinical trials in patients may indicate that the required therapeutic dose (exposure) is significantly higher than predicted. Also, higher doses (exposures) might be needed for obese patients (different volumes of distribution) or in patients with various concomitant diseases. While higher doses (exposures) may still be well tolerated, they provide a larger variety and magnitude of therapeutic effects.

Further, testing of doses higher than 2 mg is justified to account for uncertainties in translation from non-clinical to clinical information, i.e., actual pharmacokinetic or pharmacodynamics parameters may deviate from predicted values, like

- Bioavailability may be (significantly) less than predicted
- Clearance may be higher than predicted
- Half-life may be shorter than predicted
- Pharmacokinetics may be non-linear with a less than dose-proportional increase,
- Translation from pharmacodynamics data o to human

After each completed dose level, preliminary safety and pharmacokinetic data will be reviewed by the sponsor and Principal Investigator to decide on the escalation to the next planned dose level. Each dose escalation decision will be based on preliminary

- Safety and tolerability data of all available subjects on active treatment from at least 24 hours after the administration of study medication and
- Pharmacokinetic data collected in a minimum of 3 subjects on active treatment from each dose group from at least 24 hours after the administration of study medication (see Section [3.1](#)).

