##### General Risk Minimization Measures:

- Careful selection of study subjects according to in- and exclusion criteria (see Section [3.3.2](#) and Section [3.3.3](#)).
- Careful starting dose selection (see Section [1.3.1](#)).
- Decreasing escalation factors with increasing doses (see Section [1.3.3](#)).
- In the SRD-Part, for safety reasons, each dose group of 8 subjects (6 on active, 2 on placebo) will be divided into three cohorts of 2 (sentinel cohort), 3 and 3 subjects which will be separated by a time interval of at least 48 hours. The first 4 subjects of each dose group (2 subjects of the sentinel cohort and the first 2 subjects of the second cohort, i.e., random block 1) will be dosed in a fixed sequence manner (active – placebo – active – active). The remaining 4 subjects of each dose group (the last subject of the second cohort and 3 subjects of the third cohort, i.e., random block 2) will be randomised in a 3:1 ratio (active drug to placebo). While drug administration in the first cohort can be performed simultaneously (active - placebo), drug administration in the second and third cohort will be separated by at least 60 minutes. For orally administered drugs, this is usually a sufficient time interval to observe acute effects and to achieve a relevant proportion of systemic exposure.
- Extensive standard safety laboratory measurements will be performed before and after drug administration (see [Flow Chart](#) and Section [5.2.3](#)).
- Close monitoring of blood pressure (see [Flow Charts](#)).
- A thorough ECG and heart rate monitoring will be performed, including continuous ECG measurements, over 4 hours post dose to cover the anticipated period of highest drug exposure, and additional repeated single 12-lead ECGs (see [Flow Charts](#)).
- Prior to each dose escalation, a documented safety review will be performed by the Principal Investigator or an authorized deputy and the Clinical Trial Leader or an authorized deputy (see Section [3.1](#)).

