#### Stopping Rules Related to Dose Groups:

- In case of any safety concerns, as listed below but not limited to them, the trial will be mandatorily discontinued. Occurrence of severe non-serious adverse events

considered as drug-related by the investigator in 2 subjects of the same dose group (8 subjects) in the SRD-Part, or 3 subjects of the BA/ FE group (12 subjects), or occurrence of at least one drug-related serious adverse event (SAE). Moreover, dose escalation in the SRD-Part will be terminated, if more than 3 of the actively dosed subjects at one dose level show drug-related and clinically relevant adverse events of at least moderate intensity.

- Clinical apparent seizures/ convulsions in one or more subjects in the same dose group.
- EEG changes consistent with pro-convulsive activities (e.g., spike and wave) that is considered to be drug-related in two or more subjects of the same dose group.
- Clinically relevant changes in the neurological assessment indicating dose-limiting intolerance that is considered to be drug-related in one or more subjects of the same dose group.
- Dose escalation in the SRD-Part or treatment in the BA/ FE-Part will be stopped, if at least 2 subjects on active treatment at one dose level (SRD-Part) or 2 subjects in the BA/ FE-Part have relevant individual QT prolongations, i.e., a QTc increase of greater than 60 ms from baseline and/ or an absolute QT or QTc greater than 500 ms, as confirmed by a repeat ECG recording.
- Dose escalation in the SRD-Part will be stopped, if the  $C_{\max}$  or  $AUC_{0-24h}$  of at least 1 subject of one dose group increases above the following exposure thresholds or if the estimated geometric mean exposure is expected to exceed a  $C_{\max}$  of 1560 nM or an  $AUC_{0-24h}$  of 2490 nM\*h. In this case, one or two additional dose levels lower than the planned next dose level may be given, as long as the expected geometric mean exposure values of the interim dose do not exceed these exposure thresholds. Estimation will be done based on preliminary pharmacokinetic results of preceding dose groups (see Section [7.4](#))

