The groups will be dosed consecutively in ascending order, and a time interval of at least 7 days will be maintained between the last drug administration to subjects in the previous dose group and the first drug administration to subjects in the subsequent dose group. The decision to treat the next dose group will be based upon safety, tolerability and pharmacokinetic data of all the preceding dose groups. The next dose group will only be applied, if, in the opinion of the Principal Investigator (or an authorised deputy) and the Clinical Trial Leader (or an authorised deputy), no safety concerns have arisen in the preceding dose groups (i.e., no dose-limiting events occurred) and, if none of the pre-specified trial-specific stopping criteria have been met (refer to Section [3.3.4.2](#)).

A documented safety review must take place prior to each dose escalation. Furthermore, an unscheduled safety review meeting can be requested anytime by the Principal Investigator (or an authorised deputy) or the sponsor of the study (for instance, due to the occurrence of any unforeseen adverse events).

Although no formal safety review meeting will take place within a given dose group, safety will be continuously monitored during this trial, and an individual will only be dosed in the absence of any safety concern (i.e., no dose-limiting events occurred) and if none of the pre-specified trial-specific stopping criteria have been met (refer to Section [3.3.4.2](#)).

At a minimum, the following data need to be available for review to escalate to a higher dose.

- AEs in the current and preceding dose groups up to at least 48 h post dosing, including clinically relevant findings from ancillary safety testing listed below (Note: AEs may be ongoing at the time of Safety Reviews and AE information may be subject to change prior to Database Lock)
- Results from 12-lead ECG and continuous ECG monitoring in the current and preceding dose groups up to at least 48 h post dosing
- Vital signs in the current and preceding dose groups up to at least 48 h post dosing
- Clinical laboratory tests in the current and preceding dose groups up to at least 24 h post dosing
- EEG reports up to at least 24 h post dosing
- Preliminary pharmacokinetic data of at least 3 subjects on active treatment for up to at least 24 h post dosing as per Section [7.4](#)
- Check of criteria for stopping subject treatment as per Section [3.3.4.1](#)

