#### **Applicable for Amendment No. 7**

## **7.4 INTERIM ANALYSES**

### SRD-Part

No interim analysis is planned.

A preliminary analysis of safety and non-compartmental pharmacokinetic parameters ( $AUC_{0-24}$  and  $C_{max}$  of BI 1569912) provided as individual values and geometric means will be performed.

In contrast to the final PK/ PD calculations, the preliminary pharmacokinetic analysis will be based on planned sampling times rather than on actual times, regardless of whether actual times were within the time windows. Therefore, minor deviations may occur between preliminary and final results. The preliminary analysis will provide individual and mean concentration/ effect-time profiles and summary statistics of individual values without subject identification information. The preliminary results will be distributed to the investigator and the trial team.

Depending on the results of available preliminary PK/ PD analyses and the tolerability and safety of the compound, changes to the dosing schedule (e.g., additional intermediate doses), and additional PK/ PD preliminary analysis may be performed if requested by the Clinical Trial Leader, the Investigator, or Trial Clinical Pharmacokineticist. Preliminary PK/ PD results will not be reported in the CTR.

No inferential statistical interim analysis is planned. However, after completion of each dose group the investigator (or his or her deputy) is allowed to postpone further dose progression until a preliminary analysis of the data has been performed.

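### Escalation may be decided on PK from 3 of 6 active subjects, although a single subject over the exposure threshold stops escalation to the planned next dose (small gap, cheap fix)

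*Protocol*

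**What the plan says.** Two parts of the Protocol set the minimum PK for an escalation decision in the SRD part. Section 3.1 lists "Preliminary pharmacokinetic data of at least 3 subjects on active treatment for up to at least 24 h post dosing". Section 1.3.2.2 asks for "Pharmacokinetic data collected in a minimum of 3 subjects on active treatment from each dose group", while for the same decision it asks for "Safety and tolerability data of all available subjects on active treatment". The lower floor therefore applies to PK only.

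The stopping rules for dose groups in Section 1.4.7 end escalation if the Cmax or AUC0-24h "of at least 1 subject of one dose group increases above the following exposure thresholds", or if the expected geometric mean would pass 1560 nM or 2490 nM*h. The stop is not absolute: "one or two additional dose levels lower than the planned next dose level may be given", provided that their expected geometric mean stays within the limits.

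The BI 1569912 specific measures in Section 1.4.7 state the condition differently. There the next dose may be given if the predicted geometric mean is within limits *or* if no individual value of the current group is over.

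Section 7.4 plans a preliminary analysis of AUC0-24 and Cmax "provided as individual values and geometric means will be performed", without saying how many subjects it must cover.

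**The concern.** A rule triggered by one subject can be applied only to subjects whose results are in hand. It is there to catch a high individual exposure that the group mean hides. At the permitted minimum, half of the active subjects may be unseen when the next dose is approved.

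The visible limits are the dog NOAEL exposures. Section 1.3.2.1 places exposures with behavioural signs about 3-fold higher, and exposures with generalised convulsions about 5-fold (Cmax) and 6-fold (AUC0-24h) higher. If the missing result would have triggered the rule, the next group starts at the planned dose instead of an intermediate dose or none.

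**Working it through.** **Counts.** Section 3.1 gives 9 groups of 8, so 9 × 8 = 72 subjects, with 6 active and 2 placebo in each group. Under Section 1.4.7 the first four subjects are dosed in a fixed order with 3 active. The last four are randomised 3:1, which adds 4 × 3/4 = 3 active. The first block alone can therefore meet the floor. The Protocol does not say that the three must come from that block; this is what the dosing order permits. If exactly one of six is over and any three are reviewed, the chance of missing that subject at the decision is C(5,3)/C(6,3) = 10/20 = 0.50.

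**Timing.** Section 3.1 keeps at least 7 days between the last dose of one group and the first dose of the next. The last 24-h sample therefore falls at least 7 days − 24 h = 6 days before the next group starts. Only a slower assay makes a result late. Cohorts are at least 48 h apart. At that minimum spacing, a late result finds 1 active subject of the next group dosed in the first 48 h, 3 or 4 (mean 1 + 2 + 0.75 = 3.75) between 48 and 96 h, and all 6 after that.

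**Chance that an unseen subject is over the limit.** The documents give no between-subject variability and no such probability, so these are assumptions:
- lognormal exposure with gCV 20, 30 or 40%
- one binding exposure measure
- dose proportionality
- a true mean at 90% of the highest value that passes the step

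Formulas: σ = √ln(1 + gCV²); g = 0.9/step, as a fraction of the limit; p = 1 − Φ(ln(1/g)/σ). Given the true mean, the unseen three are independent of the reviewed three, so P(at least one unseen over | review passes) = 1 − (1 − p)³.

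| Step | g | gCV 20% | gCV 30% | gCV 40% |
|---|---|---|---|---|
| ×3 (0.25 to 0.75 mg) | 0.30 | <0.01% | 0.01% | 0.27% |
| ×2.67 (0.75 to 2 mg) | 0.338 | <0.01% | 0.03% | 0.72% |
| ×2.5 (2 to 5 mg) | 0.36 | <0.01% | 0.08% | 1.2% |
| ×2 (5 to 10 or 10 to 20 mg) | 0.45 | 0.01% | 1.0% | 5.6% |

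Example for ×2 at gCV 40%: σ = 0.385, ln(1/0.45)/σ = 2.07, p = 0.0191, and 1 − 0.9809³ = 0.056.

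A simulation of 2,000,000 groups at ×2 used both arms: geometric mean of the three × 2 within the limit, and none of the three over. The review passed with probability 0.822/0.732/0.674. The joint probability that it passes and an unseen subject is over was 0.01/0.7/3.8%.

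**The rows are alternatives.** A mean at 45% of the limit at 5 mg implies 90% at 10 mg and a prediction of 180% for 20 mg, which the group-mean arm blocks. Conversely, 45% at 10 mg implies 22.5% at 5 mg. There, at gCV 40%, ln(1/0.225)/0.385 = 3.87, p is about 0.00005, and the chance for three subjects is about 0.02%.

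**The case against.** The strongest reply is that existing controls leave little to go wrong. Three is a minimum, and nothing shows that it was the planned practice. Section 1.3.2.2 places the review after each completed dose level. Section 3.1 requires AE, ECG and vital-sign data to at least 48 h, so all 24-h PK samples should already be drawn by then. It also says that "an individual will only be dosed in the absence of any safety concern" and with no stopping criterion met, so a late trigger still halts further dosing. Sentinel dosing, EEG review and 72-h confinement remain. All of this stands and is why the point is minor. None of it requires the other three results before the decision, and a criterion cannot be recognised as met while its data are outstanding.

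A second reply is that the worst case is severe against the Protocol's own prediction. Section 1.2.5 predicts an AUC of 330 nM*h at 2 mg, hence 825 nM*h at 5 mg, or 33% of 2490. The same formula then gives <0.01/0.03/0.6% at 5 mg for gCV 20/30/40%. The prediction for 20 mg is 3300 nM*h, so the group-mean arm would itself stop that step. This also stands: the table gives upper-end values.

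A reader might infer that the gap matters most from 20 mg upward, where the escalation factors shrink to 1.5 and below. The documents do not support a figure there. Section 11.7 says that Amendment 7 adapted the stopping rules to new exposure limits, and the adapted text is not visible. Whether one subject still triggers a stop, and at what value, cannot be known. Amendment 7's list of changed sections names neither 1.3.2.2 nor 3.1, so only the three-subject floor can be said to continue.

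**Conclusion.** The mismatch is real but minor. Up to 20 mg, the visible text stops escalation to the planned next dose on one subject's exposure, yet lets the decision rest on half of the active subjects. The *or* in the specific measures of Section 1.4.7 adds a second, weaker version of the same rule.

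The chance that an unseen subject is over the limit is at most about 0.01/1.0/5.6% at a worst-case ×2 step, and far lower at the early steps. These figures rest on an assumed gCV and on a mean close to the highest passing value. Consequences for the next group also need an assay slower than about 6 days, for which the documents give no evidence.

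It would be wrong to conclude that subjects were in fact escalated past an unseen trigger, or that half of all triggers would go unnoticed. The 0.50 is conditional on exactly one exceedance and on only three results being in hand.

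**What to change.** In Sections 1.3.2.2 and 3.1, for every escalation step at which an individual exposure stopping rule applies, require preliminary Cmax and AUC0-24h from all actively dosed subjects of the current dose group with evaluable samples before the decision. Record any exception in the safety review minutes. In the specific measures of Section 1.4.7, align the *or* with the stopping rule, so that an exceedance on either the individual or the group-mean condition blocks the planned next dose.

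The cost is a wording change and the assay of up to 3 more subjects' samples before the decision. Those samples are already drawn, and individual values are already a planned output. The downside is a possible short delay before the next group if assay turnaround exceeds the roughly 6 days available.

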#### BA/ FE-Part

Before starting the BA/ FE-Part, a summary of safety and tolerability data (including AEs, SAEs, ARs and SARs) generated so far during the course of the trial will be submitted via a substantial amendment.

The BA/ FE part will be performed as an open-label, randomised, single-dose, intra-individual, six-sequence, three-way crossover trial in healthy male subjects in order to assess (1) the relative bioavailability of the tablet relative to PfoS (both administered under fasted conditions) and (2) the relative bioavailability of the tablet administered under fed and fasted conditions. For details, refer to Section [4.1.4](#). Subjects will be randomly allocated to the 6 treatment sequences. There will be a washout period of at least 5 days between the

treatments, i.e., the last dose in the first treatment period and the first dose in the following treatment period are separated by at least 5 days.

An overview of all relevant trial activities is provided in the [Flow Charts](#). For visit schedule and details of trial procedures at selected visits, refer to Sections [6.1](#) and [6.2](#), respectively.

### 3.2 DISCUSSION OF TRIAL DESIGN, INCLUDING THE CHOICE OF CONTROL GROUPS

#### SRD-Part

For single-rising dose trials, the sequential rising dose design described in Section [3.1](#) is viewed favourably under the provision not to expose the subjects involved to undue risks.

Single-blind conditions regarding the subject's treatment (active or placebo) are maintained within each dose group. However, subjects and investigators will be aware of the dose of drug administered. The disadvantage of the trial design is a possible observer bias with regard to the dose-dependent effects; in addition, the sequential dosing of groups could potentially result in time-related effects. However, as such effects are expected to be small relative to the differences between the doses in the broad range investigated, unbiased comparisons between treatments can still be expected.

It is standard in single rising dose trials involving healthy volunteers to include a placebo group to control for safety, tolerability, and pharmacodynamic effects of the trial medication. Each dose group consists of 8 subjects, with 6 on active treatment, and 2 on placebo. For data analysis purposes, the placebo control group will include all subjects of all dose groups treated with placebo. Six subjects per active treatment group are generally considered to be sufficient for the exploratory evaluation of pharmacokinetics.

#### BA/ FE-Part

For relative bioavailability/ bioequivalence trials, the crossover design is preferred because of its efficiency: since each subject serves as his own control, the comparison between formulations/ treatments is based on an intra-subject comparison, thus removing inter-subject variability from the comparison between formulations/treatments [[R94-1529](#)].

The open-label treatment is not expected to bias results, since the study endpoints are derived from measurement of plasma and urine concentrations of the analyte.

### 3.3 SELECTION OF TRIAL POPULATION

#### SRD-Part & BA/ FE-Part

It is planned that 84 healthy male will enter the study. The actual number of subjects entered may exceed the total of 84, if additional intermediate doses are tested (see Section [3.1](#)). Subjects will be recruited from the volunteers' pool of the trial site.

Only male subjects will be included in the trial because no data on reproductive toxicology are available at this time.

A log of all subjects enrolled into the trial (i.e. who have signed informed consent) will be maintained in the ISF irrespective of whether they have been treated with investigational drug or not.

### 3.3.1 Main diagnosis for trial entry

The study will be performed in healthy male subjects.

### 3.3.2 Inclusion criteria

Subjects will only be included in the trial if they meet the following criteria:

1. Healthy male subjects according to the assessment of the investigator, as based on a complete medical history including a physical examination, vital signs (BP, PR, RR, T), 12-lead ECG, and clinical laboratory tests
2. Age of 18 to 45 years (inclusive)
3. BMI of 18.5 to 29.9 kg/m^2 (inclusive)
4. Signed and dated written informed consent prior to admission to the study, in accordance with GCP and local legislation
5. Male subjects who meet any of the following criteria from at least 30 days before the first administration of trial medication until 30 days after trial completion:
  - Use of adequate contraception, e.g., any of the following methods (of female partners) *plus* condom: implants, injectables, combined oral or vaginal contraceptives, intrauterine device
  - Sexually abstinent
  - Surgically sterilised (including hysterectomy of female partner)
  - Postmenopausal female partner, defined as at least 1 year of spontaneous amenorrhea (in questionable cases a blood sample with FSH above 40 U/L and estradiol below 30 ng/L is confirmatory)

### 3.3.3 Exclusion criteria

Subjects will not be allowed to participate, if any of the following general criteria apply:

1. Any finding in the medical examination (including BP, PR or ECG) deviating from normal and assessed as clinically relevant by the investigator
2. Repeated measurement of systolic blood pressure outside the range of 90 to 140 mmHg, diastolic blood pressure outside the range of 50 to 90 mmHg, or pulse rate outside the range of 50 to 90 bpm
3. Any laboratory value outside the reference range that the investigator considers to be of clinical relevance, in particular, hepatic parameters (ALT, AST, total bilirubin) or renal parameters (creatinine) exceeding the ULN after repeated measurements
4. Any evidence of a concomitant disease assessed as clinically relevant by the investigator
5. Gastrointestinal, hepatic, renal, respiratory, cardiovascular, metabolic, immunological or hormonal disorders

6. Cholecystectomy or other surgery of the gastrointestinal tract that could interfere with the pharmacokinetics of the trial medication (except appendectomy or simple hernia repair)
7. Diseases of the central nervous system (including but not limited to any kind of seizures/convulsions or stroke), and other relevant neurological or psychiatric disorders
8. History of relevant orthostatic hypotension, fainting spells, or any unexplained blackouts
9. Chronic or relevant acute infections
10. History of relevant allergy or hypersensitivity (including allergy to the trial medication or its excipients)
11. Use of drugs within 30 days (or within five times of their respective elimination half-lives – whatever is longer) of planned administration of trial medication that might reasonably influence the results of the trial (including drugs that cause QT/ QTc interval prolongation)
12. Intake of an investigational drug in another clinical trial within 60 days (or within five times of the respective elimination half-life – whatever is longer) of planned administration of investigational drug in the current trial, or concurrent participation in another clinical trial in which investigational drug is administered
13. Smoker (more than 10 cigarettes or 3 cigars or 3 pipes per day)
14. Inability to refrain from smoking on specified trial days
15. Alcohol abuse (consumption of more than 24 g per day)
16. Drug abuse or positive drug screening
17. Blood donation of more than 100 mL within 30 days of planned administration of trial medication or intended blood donation during the trial
18. Sperm donation from the time of drug administration until 30 days thereafter
19. Intention to perform excessive physical activities within one week prior to the administration of trial medication or during the trial
20. Inability to comply with the dietary regimen of the trial site
21. A marked baseline prolongation of QT/ QTc interval (such as QTc intervals that are repeatedly greater than 450 ms) or any other relevant ECG finding at screening
22. A history of additional risk factors for Torsade de Pointes (such as heart failure, hypokalaemia, or family history of Long QT Syndrome)
23. Subject is assessed as unsuitable for inclusion by the investigator, for instance, because the subject is not considered able to understand and comply with study requirements, or has a condition that would not allow safe participation in the study, or is in custody by order of an authority or court of law

In addition, the following trial-specific exclusion criteria apply:

24. Any lifetime history of suicidal behaviour (i.e. actual attempt, interrupted attempt, aborted attempt, or preparatory acts or behaviour)
25. Any suicidal ideation of type 2 to 5 on the C-SSRS (i.e. active suicidal thought, active suicidal thought with method, active suicidal thought with intent but without specific plan, or active suicidal thought with plan and intent) in the past year prior to randomization

26. History or presence of epilepsy, history of more than one febrile seizure in childhood or a family history of seizures/ convulsions
27. Epileptiform abnormalities in EEG at Screening
28. History of clinically relevant head injury or trauma (e.g., associated with loss of consciousness)

In addition, the following SARS-CoV-2/COVID-19-specific exclusion criteria apply:

29. A positive PCR test for SARS-CoV-2/COVID-19 and/ or any clinical symptom suggestive for this disease at screening and on Day -3.

For study restrictions, refer to Section [4.2.2](#).

